2.13 Follow-up Procedures

Subjects who receive study treatment with the study devices will be required to complete all follow-up visits and assessments (2-Week, 4-Week and 12-Week).

2.13.1 Two-Week Post-Final Treatment Follow-Up; Day 14 ± 3 days

Clinical site staff will contact (via phone call or email) subjects two weeks after the CoolSculpting treatment and the final EMS treatment for assessment of the treatment area, pain score, and adverse events. If there are any observations reported, the study site should obtain a resolution date of the symptoms. If there is evidence that an adverse event may have occurred, the subject, at the discretion of the Investigator, may be asked to come in for an optional visit for appropriate evaluation.

ZELTIQ P/N: [REDACTED]
Protocol Number: ZAT8-003

This document and the contents hereof are considered proprietary and confidential information of ZELTIQ Aesthetics, Inc. Disclosure to unauthorized individuals or dissemination, publication or copying is prohibited without prior written consent of ZELTIQ.

2.13.2 Four-Week Post-Final Treatment Follow-Up; 4 Weeks ± 1 week;

The following evaluations will be performed at the 4-week post-treatment follow-up visit:

- i. Obtain weight.
- ii. Clinical assessment of the treatment area for any epidermal, dermal, and subcutaneous findings (e.g., erythema, bruising, swelling, pigment changes) as well as alterations in sensation (e.g., numbness, tingling).
- iii. Assessment of any adverse events.
- iv. Obtain 3-Dimensional photographs of the abdomen using Vectra or similar imaging system.
- v. Obtain photographs of the treatment area using standardized setup and settings, optional. See Section 2.14 for details.

2.13.3 Twelve-week Post Final Treatment Follow-Up Visit; 12 Weeks ± 2 weeks

The following evaluations will be performed at the 12-week post final treatment follow-up visit:

- i. Obtain weight.
- ii. Clinical assessment of the treatment area for any epidermal, dermal, and subcutaneous findings (e.g., erythema, bruising, swelling, pigment changes) as well as alterations in sensation (e.g., numbness, tingling).
- iii. Assessment of any adverse events.
- iv. Obtain 3-Dimensional photographs of the abdomen using Vectra or similar imaging system.
- v. Obtain photographs of the treatment area using standardized setup and settings. See Section 2.14 for details.
- vi. Subject to complete Global Aesthetic Improvement Scale.

2.13.4 Optional Follow-Up Evaluations (up to 4 within study period)

The full evaluation is not required at optional follow-up visits; the extent of the assessment will be at the discretion of the Investigator.

Table 3 summarizes the study schedule and events at each visit.

Table 3. Schedule of Visits

	Screening (< 1hr)	Photo Visit (<1hr)	EMS Treatment #1 (<2hrs)	EMS Treatment #2 (<2hrs)	EMS Treatment #3 (<2hrs)	EMS Treatment #4 (<2hrs)	CoolSculpting Treatment (<4hrs)	2-Wk Post Tx Phone Follow-Up (<30 min)	4-Wk Post-Tx Follow-Up 12-Wk Post- Tx Follow-Up<br (<="" 1="" hr)<="" th=""/>Optional Follow- Up*****		12-Wk Post- Tx Follow-Up Optional Follow- Up*****	Optional Follow- Up*****
Time Frame	Day -60 to 0	Day -30 to 1	Day 0	Week 1	Week 2	Week 2	Day 0- Day 10 ±3 days	Week 2-3****	(4 ± 1 weeks)	(12 ± 2 weeks)	Open
Informed Consent***	X										
Eligibility Criteria	X		X	X	X	X	X				
Medical History	X										
Tx Site Assessment	X		X	X	X	X	X		X	X	
Height	X										
Weight	X	X	X				X		X	X	
BMI	X										
3D Photography		X				X			X	X	
Standardized Photography		X				X [#]			X [#]	X	
CoolSculpting							X ^{**}				
EMS			X*	X*	X*	X*					
Pain Assessment			X	X	X	X	X	X	X	X	
AE Assessment			X	X	X	X		X	X	X	
Subject GAIS										X	

* EMS treatment visits 1, 2, 3, 4 apply to Cohorts 1, 2 and 4 only.

** Cohort 2 after EMS and Cohort 3.

*** Informed Consent to be signed by subject prior to the collection of any data or initiation of any study procedures.

**** 2-week F/U timing is dependent on cohort assignment.

***** Investigator discretion as to timing and extent of follow-up assessment for optional visits.

Optional

2.14 Assessments

Study-related assessments are described below.

2.14.1 Global Aesthetic Improvement Scale (GAIS-Independent)

Independent physician(s) experienced in body contouring treatment will be asked to rate the improvement observed in the subject's treated area between 12-week post final treatment images and baseline images, using the Global Aesthetic Improvement Scale:

- 3 = Very much improved
- 2 = Much improved
- 1 = Improved
- 0 = No change
- -1 = Worse
- -2 = Much worse
- -3 = Very much worse

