2.6 Sample Size

A maximum of sixty (60) subjects will be included in the study.

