2.14.3 Photography

Three-Dimensional (3-D) photography will be used in this evaluation. 3-D photography may be performed using a commercially available photography system, such as the Canfield VECTRA or similar device.

In addition, standardized photos of the treatment areas will be obtained at pre-treatment and 12-week visits, using standardized setup, lighting, and camera settings

to ensure consistency. All standard photographs will be captured at fixed angles and posture. Using a series of pre-determined markings on the floor, the photographer will position the camera at the pre-determined reference points to ensure that the reproduction ratio and focal distance are maintained throughout the image series during the study. Subjects will use a Foot Positioning Guide (FPG) for each body angle. During follow-up visits, the photographer will re-align subjects on the FPG by referencing baseline images. The photos will be used in the Independent GAIS evaluation

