2.15 Endpoints

2.15.1 Primary Endpoints

The primary endpoints of the study will be defined as follows:

- *Efficacy endpoint:* Comparison of pre-treatment and 12-week post-final treatment photographs to assess visible changes in the abdomen.
- *Safety endpoint:* Incidence of unanticipated adverse device effects (UADE). It is expected there will be zero UADEs.

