2.16 Statistical Analysis Plan

2.16.1 Statistical Methods: Overall Plan

Data will be summarized based on the nature of the data. Dichotomous (e.g., gender, independent photographic review) and ordinal (e.g., Fitzpatrick Skin type) data will be tabulated by category. The mean, standard deviation, maximum and minimum will be tabulated for continuous data (e.g., age). The significance level will be two-sided 0.05 for all statistical tests.

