2.16.2 Analysis Population

Analysis Populations are defined as following:

Per-protocol Population (PP):

The Per-protocol Population will consist of all treated subjects followed for 12 weeks and with weight change of no more than five percent (5%) of total body weight at the time the 12-week images are taken compared to the weight taken at the photo visit. Since significant weight change will affect the images, the primary efficacy analysis will be performed based on this study population. Subjects who do not complete treatment will not be included in the efficacy analyses.

As-Treated Population (AT):

This population consists of all treated subjects regardless of weight change etc.

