2.16.3 Endpoint Analysis

Primary Endpoints:

The primary efficacy endpoint will be evaluated by a comparison of pre-treatment and 12-week post-final treatment photographs to assess visible changes in the abdomen. Independent physician(s) experienced in body contouring treatment will be asked to rate the improvement observed in the subject's treated area between 12-week post final treatment images and baseline images, using the Global Aesthetic Improvement Scale.

The primary safety endpoint is the incidence of Unanticipated Adverse Device Effects (UADE). The number and percentage of subjects experiencing each AE Term will be descriptively summarized.

ZELTIQ P/N: [REDACTED]
Protocol Number: ZA18-003

Secondary Endpoints:

Circumference

Circumference measurements obtained using 3-D imaging pre-treatment and at the 12-week post-final visit will be analyzed using the imaging manufacturer's software tools.

Global Aesthetic Improvement Scale

At 12-weeks post-final treatment, the subject will be asked to rate the improvement observed in the treated area using the Global Aesthetic Improvement Scale. The questionnaire is scored on a 7-point scale with 3 = Very much improved, 2 = Much improved, 1 = Improved, 0 = No change, -1 = Worse, -2 = Much worse, and -3 = Very much worse.

The number and percentage of subjects will be summarized for each possible point grade of the survey at 12 weeks. The percentage of subjects who noted some improvement will be tabulated, and the corresponding exact 95% confidence interval (per binomial distribution) will be calculated.

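### Nothing in the plan requires masking of image order, visit or cohort for the photo rating that carries the primary efficacy endpoint

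*Combined protocol and SAP*

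**What the plan says.** Section 2.15.1 defines the primary efficacy endpoint as "Comparison of pre-treatment and 12-week post-final treatment photographs to assess visible changes in the abdomen". Section 2.14.1 turns this into a rating on a symmetric seven-grade scale from -3 to 3, in which the raters are to "rate the improvement observed in the subject's treated area between 12-week post final treatment images and baseline images", and section 2.16.3 repeats it: "Independent physician(s) experienced in body contouring treatment will be asked to rate the improvement observed". The number of raters is left open.

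Section 2.14.3 fixes angle, posture, lighting and camera position, and adds: "The photos will be used in the Independent GAIS evaluation". Section 2.16.2 defines a per-protocol set that limits weight change to 5% and says that "the primary efficacy analysis will be performed based on this study population". Table 2 in section 2.9 lists four cohorts: EMS alone, EMS then CoolSculpting, CoolSculpting alone, and CoolSculpting then EMS. There is no untreated or sham group.

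On the summary of the rating, section 2.16.1 says: "Dichotomous (e.g., gender, independent photographic review) and ordinal (e.g., Fitzpatrick Skin type) data will be tabulated by category". The primary-endpoint paragraph of 2.16.3 adds no cut-off, percentage or interval. For the subject GAIS, on the same seven grades, 2.16.3 plans counts and percentages per grade and then: "The percentage of subjects who noted some improvement will be tabulated, and the corresponding exact 95% confidence interval (per binomial distribution) will be calculated".

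**The concern.** The rating task names the two images by visit and asks about improvement. A rater who knows which image is the later one, or which cohort the subject was in, may lean towards the expected direction when a pair shows little change. An error that runs in one direction adds to the improved share and stays out of the worse share. An exact binomial interval does not cover it. With random order, the same error would fall on both sides, and the share scored worse would give a rough idea of the noise.

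Because every cohort is treated, no group shows what the rating would look like without treatment. Knowledge of cohort could also colour any informal comparison between the modalities. At stake is how far the main efficacy result of this feasibility study can be taken at face value.

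**Working it through.** The plan gives no figure on this point to reproduce. The check is a comparison of sections, followed by an illustration on assumed inputs.

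**1. What each section controls**

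- 2.14.1 and 2.16.3: who rates, which two time points are compared, and the scale. They do not say how the pair is presented.
- 2.14.3: how the standardized photographs are taken.
- 2.16.2: weight change, as a confounder of the images.
- 2.14.4 and 2.16.3: circumference calculated by software from 3-D images. This does not depend on the photo raters, but it is a secondary endpoint.

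None of these governs what a rater knows when scoring. Sections 2.14.1, 2.14.3, 2.16.1 and 2.16.3 carry no redaction marks, so a masking statement does not appear to have been blacked out there.

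**2. Possible size (all inputs assumed)**

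Let t = 0.40 be the share truly improved and always scored so, u = 0.60 the share unchanged, and none truly worse. Let c be the share of unchanged pairs miscalled (0.10 to 0.30), and f the share of miscalls that favour the later image (0.70 to 1.00 unmasked, 0.50 masked). The same c is used with and without masking.

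Improved = t + u × c × f. Worse = u × c × (1 − f).

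- Low case, unmasked: 0.40 + 0.60 × 0.10 × 0.70 = 44.2% improved; 0.60 × 0.10 × 0.30 = 1.8% worse.
- Low case, masked: 0.40 + 0.60 × 0.10 × 0.50 = 43.0% improved; 3.0% worse.
- High case, unmasked: 0.40 + 0.60 × 0.30 × 1.00 = 58.0% improved; 0.0% worse.
- High case, masked: 0.40 + 0.60 × 0.30 × 0.50 = 49.0% improved; 9.0% worse.

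Masking removes 44.2 − 43.0 = 1.2 points in the low case and 58.0 − 49.0 = 9.0 points in the high case. Symmetric noise of 3.0 to 9.0 points above the assumed 40% remains. Improved minus worse is 42.4 to 58.0 points unmasked and 40.0 masked. The last figure follows from setting f to 0.50 and is not evidence about this trial.

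**3. Against sampling error**

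Section 2.6 says only: "A maximum of sixty (60) subjects will be included in the study". Cohort sizes are not stated, so assume 60/4 = 15, or 60/3 = 20 if Cohort 4, which re-uses Cohort 3 subjects, adds no new people. Exact (Clopper-Pearson) 95% intervals:

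- 8/15 = 53.3%: 26.6% to 78.7%, half-width (78.7 − 26.6)/2 = about 26 points.
- 10/20 = 50.0%: 27.2% to 72.8%, half-width (72.8 − 27.2)/2 = about 23 points.

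A shift of 1.2 to 9.0 points is smaller than either half-width. It would not shrink with more subjects, but the study stops at 60.

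**4. The summary of the rating**

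Section 2.16.1 puts independent photographic review among the dichotomous examples. The only independent photo rating visible in the documents has seven grades and no stated cut-off. The sentence on the percentage and exact interval sits under the secondary endpoints and concerns what subjects noted, so it does not extend to the physicians' rating.

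**The case against.** The strongest reply is that this is an argument from silence. Naming the two time points does not say how the images are shown, and the wording is compatible with coded pairs in random order. No rater form or reading instructions are among the documents. That stands: a reader might infer that the raters will be unmasked, or that the primary result will be biased, and the documents support neither. They support only that masking is not required.

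Credit is also due to what is there. Raters described as independent are plausibly separate from the treating staff, although the word says who rates and not what they see. The 3-D circumference is a partial cross-check, so the point about inseparable bias holds for the rating and not for the study as a whole.

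The illustration rests wholly on assumed inputs and does not model knowledge of cohort. The study is a non-randomized feasibility study with no efficacy threshold or named efficacy test, so no pass/fail decision turns on the shift.

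A reader might also infer that the SAP misclassifies the GAIS, or leaves the primary rating without any summary. Neither reading is secure. Section 2.16.1 does not name the GAIS in that list, its term could mean improved versus not improved, and the exploratory list in 2.15.3 is blank in this copy and might hold a yes/no review. The same sentence does provide a tabulation by category. What is missing is an explicit cut-off and an interval.

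**Conclusion.** The point holds in a limited form. The visible plan does not require masking of image order, visit or cohort for its primary efficacy rating, and no untreated group is available to show a lean towards the later image. The documents do not allow the size to be estimated. Under the assumptions above, the part that masking would remove is about 1 to 9 points, below the sampling error of a single cohort of an assumed 15 to 20 subjects. The case for change is that the safeguard costs very little, not that a large bias has been shown. The data-type label and the missing interval are a minor note: as written, a secondary rating has a fuller planned summary than the primary one on the same scale.

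**What to change.** In section 2.14.1, state that each baseline/12-week pair is shown in random left/right order with date, visit and cohort removed, that the rater scores the right image against the left on the existing symmetric scale, and that programming restores the sign. If this is already intended, one sentence saying so is enough.

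As a minor addition in section 2.16.3, apply the subject-GAIS summary to the independent GAIS by cohort: count and percentage at each grade, percentage graded 1 or higher, and exact 95% confidence interval. Align the example in 2.16.1 with this by listing the independent GAIS as ordinal.

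The cost is coded image labels, a sign flip in programming and a few lines of text, with no extra raters, images or visits. There are downsides. The rater's task changes slightly, from scoring improvement to scoring one image against the other. The improvement rate may come out lower. Masking removes only the directional part of rater error, and raters may still guess the order when change is obvious.

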2.14.2 Global Aesthetic Improvement Scale (GAIS-Subject)

At 12-weeks post-final treatment, subjects will be asked to rate the improvement observed in the treated area using the Global Aesthetic Improvement Scale:

- 3 = Very much improved
- 2 = Much improved
- 1 = Improved
- 0 = No change
- -1 = Worse
- -2 = Much worse
- -3 = Very much worse

2.14.3 Photography

Three-Dimensional (3-D) photography will be used in this evaluation. 3-D photography may be performed using a commercially available photography system, such as the Canfield VECTRA or similar device.

In addition, standardized photos of the treatment areas will be obtained at pre-treatment and 12-week visits, using standardized setup, lighting, and camera settings

to ensure consistency. All standard photographs will be captured at fixed angles and posture. Using a series of pre-determined markings on the floor, the photographer will position the camera at the pre-determined reference points to ensure that the reproduction ratio and focal distance are maintained throughout the image series during the study. Subjects will use a Foot Positioning Guide (FPG) for each body angle. During follow-up visits, the photographer will re-align subjects on the FPG by referencing baseline images. The photos will be used in the Independent GAIS evaluation

2.14.4 Circumference Measurements

Subjects will undergo 3-D imaging. The imaging will be used to calculate abdomen circumference using the 3-D imaging manufacturer's software tools.

2.15 Endpoints

2.15.1 Primary Endpoints

The primary endpoints of the study will be defined as follows:

- *Efficacy endpoint:* Comparison of pre-treatment and 12-week post-final treatment photographs to assess visible changes in the abdomen.
- *Safety endpoint:* Incidence of unanticipated adverse device effects (UADE). It is expected there will be zero UADEs.

2.15.2 Secondary Endpoints

The secondary endpoints in the study are:

- Reduction in abdominal circumference as measured by 3-Dimensional imaging.
- Subject Global Aesthetic Improvement Scale at 12-weeks post-final follow-up visit.

2.15.3 Exploratory Assessments:

Additional analyses, which may be performed, include:

2.16 Statistical Analysis Plan

2.16.1 Statistical Methods: Overall Plan

Data will be summarized based on the nature of the data. Dichotomous (e.g., gender, independent photographic review) and ordinal (e.g., Fitzpatrick Skin type) data will be tabulated by category. The mean, standard deviation, maximum and minimum will be tabulated for continuous data (e.g., age). The significance level will be two-sided 0.05 for all statistical tests.

2.16.2 Analysis Population

Analysis Populations are defined as following:

Per-protocol Population (PP):

The Per-protocol Population will consist of all treated subjects followed for 12 weeks and with weight change of no more than five percent (5%) of total body weight at the time the 12-week images are taken compared to the weight taken at the photo visit. Since significant weight change will affect the images, the primary efficacy analysis will be performed based on this study population. Subjects who do not complete treatment will not be included in the efficacy analyses.

As-Treated Population (AT):

This population consists of all treated subjects regardless of weight change etc.

2.16.3 Endpoint Analysis

Primary Endpoints:

The primary efficacy endpoint will be evaluated by a comparison of pre-treatment and 12-week post-final treatment photographs to assess visible changes in the abdomen. Independent physician(s) experienced in body contouring treatment will be asked to rate the improvement observed in the subject's treated area between 12-week post final treatment images and baseline images, using the Global Aesthetic Improvement Scale.

The primary safety endpoint is the incidence of Unanticipated Adverse Device Effects (UADE). The number and percentage of subjects experiencing each AE Term will be descriptively summarized.

ZELTIQ P/N: [REDACTED]
Protocol Number: ZA18-003

Secondary Endpoints:

Circumference

Circumference measurements obtained using 3-D imaging pre-treatment and at the 12-week post-final visit will be analyzed using the imaging manufacturer's software tools.

Global Aesthetic Improvement Scale

At 12-weeks post-final treatment, the subject will be asked to rate the improvement observed in the treated area using the Global Aesthetic Improvement Scale. The questionnaire is scored on a 7-point scale with 3 = Very much improved, 2 = Much improved, 1 = Improved, 0 = No change, -1 = Worse, -2 = Much worse, and -3 = Very much worse.

The number and percentage of subjects will be summarized for each possible point grade of the survey at 12 weeks. The percentage of subjects who noted some improvement will be tabulated, and the corresponding exact 95% confidence interval (per binomial distribution) will be calculated.

2.17 Protocol Adherence

The study Investigators are responsible for performing the study in compliance with the protocol. Non-adherence to the protocol is to be classified as a protocol violation or protocol deviation as defined below.

Protocol Violation

Non-adherence to the protocol that may result in significant additional risk to the subject (e.g., enrollment of a subject who does not meet the study criteria). Or, non-adherence to Good Clinical Practices (GCP) that may impact patient safety (e.g., failure to obtain proper consent prior to performing study procedures). Violations should be reported to the study Sponsor within 5 working days and reported to the IRB per IRB guidelines.

Protocol Deviation

Non-adherence to study procedures which does not result in additional risk to the subject (e.g., subject missed visit). Protocol deviations are not required to be reported to the IRB; however, they must be recorded on the study case report forms and may be reported and reviewed in conjunction with the progress report as part of the annual review process.

ZELTIQ P/N: [REDACTED]
Protocol Number: ZA18-003

2.18 Adverse Events

Adverse events (AEs) will be assessed continuously throughout the study. An adverse event is defined as any untoward medical occurrence in a participant, regardless of whether the event is related to the device.

All AEs and device deficiencies will be recorded on the corresponding CRF for the subject.

Adverse Device Effect (AE)

Any sign, symptom, or disease in a study participant that occurs during the course of a clinical trial that is determined by the Investigator to have a causal relationship or possible causal relationship with the device under investigation.

Device Deficiencies

A device deficiency is defined in accordance with ISO 14155 as inadequacy of a medical device including issues with respect to its identity, quality, durability, reliability, safety, or performance. Device deficiencies include malfunctions, use errors, and inadequate labeling.

If a device deficiency occurs, the investigational site will document the event using the CRF. Device deficiencies will be documented throughout the study and appropriately managed and reported to regulatory authorities and IRBs as required by Federal regulations.

Serious Adverse Event (SAE)

Any untoward medical occurrence in a participant, regardless of whether the event is related to the device that:

- a. results in death;
- b. results in a life-threatening illness or injury;

The term life threatening in the definition of serious refers to an event in which the participant was at risk of death at the time of the event. It does not refer to an event, which hypothetically might have caused death, if it were more severe.

- c. results in a permanent impairment of a body structure or body function;
 - o Impairment of body function means a substantial disruption of a person's ability to conduct normal life functions.
 - o This definition is not intended to include experiences of relatively minor medical significance such as uncomplicated headache, nausea, vomiting, diarrhea, influenza, and accidental trauma (e.g., sprained ankle) which may interfere with or prevent everyday life functions but do not constitute a substantial impairment.

- d. requires in-patient hospitalization or prolongation of existing hospitalization;
 - o In general, hospitalization signifies that the participant has been detained (usually involving at least an overnight stay) at the hospital or emergency ward for observation and/or treatment that would not have been appropriate in the physician's office or outpatient setting. Complications that occur during hospitalization are AEs. If a complication prolongs hospitalization or fulfills any other serious criteria, the event is serious. When in doubt as to whether hospitalization occurred or was necessary, the AE should be considered serious. Hospitalization for elective treatment of a pre-existing condition that did not worsen from baseline is not considered an AE.
- e. results in medical or surgical intervention to prevent impairment to body structure or function;
- f. results in fetal distress, fetal death, or a congenital abnormality/birth defect.

Time Period and Frequency for Collecting AE and SAE Information

All AEs and SAEs from the signing of the ICF until the follow-up visit will be collected at the time points specified in the schedule of activities, and as observed or reported spontaneously by study participants.

Medical occurrences that begin after signing of informed consent and before administration of study treatment will be recorded on the Medical History/Current Medical Conditions section of the CRF not the AE section.

Unanticipated Adverse Device Effect (UADE)

Any serious adverse effect on health and safety or any life-threatening problem or death caused by, or associated with a device, if that effect, problem, or death was not previously identified in nature, severity, or degree of incidence in the investigational plan or application, or any other unanticipated serious problem associated with a device that relates to the rights, safety, or welfare of participants.

The Investigator shall be responsible for determination of the causal relationship of all adverse events to the device and/or procedure. The Principal Investigator is responsible for monitoring the safety of the participants enrolled.

Reportable Incidents

ZELTIQ P/N: [REDACTED]
Protocol Number: ZA18-003

Serious adverse events (SAEs) and unanticipated adverse device effects (UADEs) must be recorded and reported to the manufacturer of the study device and to the Sponsor or designee within 24 hours of knowledge of the event.

Sponsor Contact:

[name]
Director, Clinical Trial Management
ZELTIQ Aesthetics, an Allergan affiliate
[name]
[name]
[REDACTED]

A full reporting of the event shall be provided within 10 working days of the event. The Sponsor is then responsible for notifying the IRB, as required.

Other adverse events, deemed by the investigator to be non-serious, should be provided to the Sponsor as soon as possible and not later than 1 week after knowledge of the event. This will be forwarded to the Product Surveillance team within 24 hours of receipt by the Sponsor Contact.

Additional information obtained by the Clinical Site regarding any adverse event, both serious and non-serious, will be reported to the Sponsor within 24 hours of awareness.

3. Study Management and Quality Control

